HIPAA	Health Insurance Portability and Accountability Act
ICC	Intra-class correlation
ICER	Incremental cost-effectiveness ratio
ICF	Informed Consent Form
ICH	International Conference on Harmonisation
ISM	Independent Safety Monitor
IRB	Institutional Review Board
ITT	Intention-to-treat
MAR	Missing at Random
MRC	Methodology Research Core
Ν	Number (typically refers to participants)
NIDCR	National Institute of Dental and Craniofacial Research, NIH, DHHS
NIH	National Institutes of Health
ОСТОМ	Office of Clinical Trials Operations and Management
OHI-MIS	Simplified Oral Hygiene Index – Maxillary Incisor

[figure not shown]
OHRP	Office for Human Research Protections
PHI	Personal Health Information
PI	Principal Investigator
PROMIS	Patient-Reported Outcomes Measurement Information System
RA	Research Assistant
SAE	Serious Adverse Event
TOST	Two One Sided Tests
UCSF	University of California at San Francisco
UIC	University of Illinois at Chicago
US	United States
WIC	Supplemental Nutrition Program for Women, Infants, and Children

PROTOCOL SUMMARY

Title:	COordinated Oral health Promotion (CO-OP) Chicago Randomized Controlled Trial
Précis:	COordinated Oral health Promotion (CO-OP) Chicago will bring together a team of clinical pediatricians and dentists, researchers, health psychologists, and policy experts to rigorously test the ability of an oral health promotion intervention to improve tooth brushing behaviors for children under the age of 3 years old. The primary intervention will be family-focused oral health education and support from community health workers (CHWs) delivered to families over one year. Participating study families will be recruited from pediatric primary care medical clinics and community social service centers (Women Infant and Children [WIC] Centers). Sites will be cluster randomized to intervention (CHW services) or usual care. Data on self-reported brushing frequency, plaque score, and other oral health behaviors will be collected at baseline, 6-months, and 12-months. The primary analysis will assess for differences in brushing frequency and plaque score between the two arms at 12-months.
Objectives:	The primary study objective is to evaluate the efficacy of a one- year oral health CHW intervention, compared to usual care, to improve self-reported brushing frequency and observed plaque score in low income urban children under the age of 3 years old. This is achieved by offering CHW intervention to half of participating families and comparing them to families receiving usual care.
	Outcomes: frequency of brushing child's teeth, amount of plaque on child's teeth (plaque score)
	The first exploratory objective is to determine if child tooth brushing behaviors are different in families whose oral health CHW is clinic-based compared to community-based. This is achieved by recruiting families from both primary care medical clinics and WIC centers. Sites are randomized to oral health CHW intervention (on the site level) or usual care to allow for an equal distribution of families receiving intervention and usual care in clinics and WIC centers.
	Outcomes: frequency of brushing child's teeth, amount of plaque on child's teeth (plaque score)

	The second exploratory objective is to determine the cost effectiveness of the CHW intervention compared to usual care. Outcomes: System-level (program) costs
Population:	Participants are caregiver/child dyads in Cook County, IL. We anticipate enrolling 420 caregiver/child dyads (18-23 from each site). To qualify, children must be aged 6-36 months with a minimum of two central maxillary incisors at least 50% erupted. Caregivers will be mostly female. Children will be equally male/female. Families will be almost entirely of African- American race and Hispanic ethnicity.
Phase:	II
Number of Sites:	20 sites: 10 primary care medical clinics and 10 WIC centers.
Description of Intervention:	CHWs trained in oral health will be assigned to half of the sites. Participants in these sites will be offered four in-person visits and follow-up phone calls over 12-months. These visits can occur at the location of the family's preference (recruitment site, home, or mutually-agreed upon other location). A core curriculum of oral health topics will be covered during visits, with an emphasis on developing and sustaining healthy oral health management routines for the entire family.
Study Duration:	34 months
Subject Participation Duration:	12 + 3 months.
Estimated Time to Complete Enrollment:	12 months

Schematic of Study Design:

2 INTRODUCTION: BACKGROUND INFORMATION AND SCIENTIFIC RATIONALE

2.1 Background Information

Almost half of children 11 years old and younger suffer from dental caries, making caries one of the most common chronic diseases of childhood.¹ Low income and minority children bear a disproportionate portion of this burden and its associated morbidity.²⁻⁵ Caries prevalence in Illinois and Chicago exceeds national figures, and Chicago area children have a high prevalence of untreated caries.⁶ Factors that contribute to caries in children include insufficient fluoride exposure, unhealthy diets, and poor oral hygiene.⁷⁻⁸

Community health workers (CHWs) are frontline public health workers who serve as liaisons between health and social services and community residents to facilitate access to services and improve the quality and cultural competence of service delivery.⁹ CHWs typically provide health education, information, assistance with services, and build individual and community capacity for health.¹⁰ CHWs have been a part of health promotion and disease prevention efforts in US communities for several decades. CHW programs aim to address the health needs of under-served populations by training community members to be health educators who can reach their friends and neighbors effectively.¹¹⁻¹³ The basic rationale for this approach with underserved and hard-toreach populations is that CHWs live in the same communities and have struggled with many of the same issues as their neighbors and thus share with the target population a similar base of knowledge and experiences.¹²⁻¹³ CHWs utilize a model that empowers community members to identify their own needs and implement their own solutions with support from medical providers, which leads to improved community and personal selfefficacy.¹⁴⁻¹⁶ There has been tremendous national interest in CHW interventions. This interest in part comes from an increasing number of studies supporting a role for CHW interventions in the improvement of health outcomes.¹⁷⁻²⁰ However there are limited data to support CHW intervention efficacy upon child oral health outcomes or associated family behaviors.²¹⁻²⁵

COordinated Oral health Promotion (CO-OP) Chicago will test the efficacy of a familyfocused CHW oral health intervention to improve tooth brushing behaviors for young children. CHWs will be based out of two settings: a clinical setting and a community setting. The results of this study will inform the need for and design of future research and programs that include oral health specific CHWs.

2.2 Rationale

The primary hypothesis this study tests is as follows: Participants receiving the oral health CHW intervention will have improved oral health behaviors, as measured using self-reported brushing frequency and observed plaque score, at 12-months compared to participants receiving usual care.

Caregiver directed oral health education has been shown to have a positive effect on knowledge, intended behavioral change (including snacking and sugar intake), and

caries prevalence.^{21, 26-27} CHWs deliver education, social support and navigation services, which are important for low income families, but it remains unclear if oral health CHWs can influence knowledge and behaviors.^{13,28}

The primary goal of CO-OP Chicago is to use a rigorous study design to determine the ability of a CHW-delivered oral health intervention to improve oral health behaviors, specifically tooth brushing, in high risk low income families. If the outcomes of this study indicate a potential utility for the CHW intervention, future research will investigate the impact of the intervention on caries development. This study's exploratory aim also will determine if future CHW studies need to further investigate setting of CHW intervention delivery.

CHWs typically work out of either a clinical location or a community agency. Therefore CO-OP Chicago places CHWs in both types of location as their primary base. Ten pediatric primary care clinics that serve low income families were recruited, as well as 10 Women Infant and Children (WIC) centers which are social service centers where families receive free formula and food. CHWs can meet with families in their clinic/WIC center, participant homes, or a mutually-agreed upon location. The CHW intervention will be delivered over four in-person visits within one year; this "dosage" was chosen in order to align with well child medical checks and WIC center appointments (typically every 3 months). Four visits per year has also been found in other disease areas to be both acceptable to families and associated with cost savings.²⁹ The one-year duration was chosen because completing dental clinic visits or making behavioral changes can take months. In addition, the CHWs often need to spend entire visits on social issues such as communication or access. These are important time investments because they allow the families to gain resources and skills to make changes related to oral health. Another advantage to a year-long intervention is that it allows for reinforcement after mastering a behavior (such as brushing daily) in order to maintain that behavior long term.

The study population was chosen for several reasons. While caries can be treated, the ultimate goal in pediatrics is primary prevention. Families with children under the age of 3 years old were chosen in order to establish healthy behaviors for a lifetime.³⁰ The recruitment sites serve low income, predominantly minority families whose rates of caries development are higher than the general population.³¹⁻³²

2.3 Potential Risks and Benefits

There are no known benefits to this research. The risks are mainly related to discomfort and confidentiality, as described in Section 2.3.1.

2.3.1 Potential Risks

Caregivers and children who participate in this study may experience discomfort with responding to questions, having their home and brushing observed, and having their children's teeth examined. They may not be comfortable with research staff or CHWs in their home. Staff will assure families that individual responses to study questionnaires

and individual oral exam and behavioral observation data collected for the study will not be shared with social service agencies, organizations, and people outside the study.

There is a risk of loss of confidentiality for all study participants. Precautions will be in place to minimize this risk, such as collecting only minimal identifying information and storing data collection documents in locked cabinets (located in locked offices), using unique study codes for participants, using encrypted computers, and maintaining electronic data files on a password-protected computer drive. Individual identifier numbers that are linked to participant contact information will be stored separately from the data. Compliance with all IRB regulations concerning data collection, data analysis, data storage, and data destruction will be strictly observed.

2.3.2 Potential Benefits

All study participants will be offered oral health CHW services either during the study or after its completion; however, it has not been demonstrated to date if this is a beneficial intervention. Therefore there are no known direct benefits to study participants. This study is intended to determine the efficacy of a CHW-delivered oral health intervention, which may add to the body of knowledge about interventions that improve children's oral health.

3 OBJECTIVES

3.1 Study Objectives

The primary study objective is to evaluate the efficacy of a one-year oral health CHW intervention, compared to usual care, to improve self-reported brushing frequency and observed plaque score in low income urban children under the age of 3 years old.

The study's first exploratory aim is to determine if the oral health CHW intervention impact on child tooth brushing behaviors varies when the CHWs are based out of a medical clinic compared to a community WIC center.

The second exploratory aim is to determine the cost effectiveness of the CHW intervention compared to usual care at the system-level.

3.2 Study Outcome Measures

Outcome measures will be collected by research assistants at baseline, 6 months and 12 months. Outcomes are a mixture of self-report, clinical assessment, observations of behaviors and the home environment, and cost data. These are described in detail in Appendix B.

3.2.1 Primary

This study has two primary assessment measures of tooth brushing behavior.

- (1) Caregiver self-report of child tooth brushing frequency: This is an ordinal variable (<1 time/day, 1 time/day, 2 or more times/day). The goal of the intervention is to increase the frequency of participants reporting "2 or more times/day".

- (2) Dental plaque: See Appendix C for the full plaque score protocol. Using disclosing solution, plaque will be observed on the buccal surfaces of teeth #D, E, F and G. Amount of plaque is reported using the Oral health Index - Maxillary Incisor Score (OHI-MIS) which is a continuous variable, range 0 to 3.

3.2.2 Secondary

The secondary measures (shown in detail in Appendix B) are organized into several domains.

Oral health behaviors include duration of brushing and caregiver assistance with brushing, age started brushing, amount of toothpaste, and type of toothpaste (fluoride or no fluoride.) Whenever possible, self-reported behaviors will also be observed. Child access to appropriate timely dental care will also be assessed. CHWs will target all these behaviors in the intervention. In analyses, these variables will represent additional components of healthy daily oral care behaviors for children.

CHWs work by improving knowledge, self-efficacy, and building self-management skills and supports.¹⁴⁻¹⁶ Therefore we will measure caregiver knowledge, self-efficacy, and child and caregiver oral health quality of life. We will also measure caregiver psychological functioning, social support, and family functioning using the NIH PROMIS measures and the CHAOS scale.³³⁻³⁶ These variables will be used in analyses to understand changes, or lack of, in the primary outcomes.

A range of risk factors for caries and associated oral health behaviors will be measured as covariates. These include exposure to sugar sweetened beverages, weaning behaviors, prior caries experience, sibling severe caries experience, and caregiver oral health behaviors and access. Medical risk factors such as child co-morbidities, medications, and weight will be assessed.

Data will also be collected on the CHW intervention, both to inform intervention fidelity and generate cost estimates. Cost estimates are only relevant for the CHW intervention arm, because the usual care arm has no additional costs. Cost estimates will only be collected on the system-level. While individuals may ultimately incur some costs, the intervention is designed to minimize these. (Visits in clinics and WICs will be aligned with visits they already plan to attend for healthcare or WIC services. Home visits will be arranged around work schedules and require no travel for participants.)

System-level costs: CHW time for visit set-up, travel, and delivery will be determined. Duration of CHW visits will be recorded (using case report forms), as well as the time needed for scheduling (weekly estimates with supervisor) and for transportation to home visits (mileage logs). This will be multiplied by CHW salary/benefits. The mileage costs will be recorded from mileage logs. CHW supplies and equipment (educational materials, phones, computers, and any other items) will be obtained through expense reports.

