Three to four CHWs (3.0 FTE) will be hired. Once hired, CHWs will undergo additional training. If the CHWs have not previously worked or been trained as CHWs, they will undergo the UIC Coordinated Healthcare for Complex Kids (CHECK, *https://www.mycheck.uic.edu/* basic CHW training which was designed by [name] and is supervised currently by [name]:

Topics	Duration	
CHECK Overview: Medicare and Medicaid overview, CMS innovations awards, Inappropriate healthcare use, Goals and activities of CHECK	1 hour 30 minutes	
Health and Disease Overview: Diabetes type 1, Prematurity, Sickle cell disease, Asthma	1 hour	
Building Relationships and Motivational Interviewing: Trust, Communication, Coping and support, Respect and patient-centeredness	1 hour	
Self-Advocacy: Advocating for yourself, teaching patients to self-advocate	30 minutes	
Teamwork and Conflict Resolution: Teamwork, Conflict resolution	30 minutes	
Managing Transitions: Transitioning from adolescence to adulthood, Transitioning from pediatric to adult care, Hospital to home	30 minutes	

CHECK Basic CHW Training Program

Home Visitation: Why home visits, Preparing for a home visit, Safety, Home visit etiquette, Building trust, Mandatory reporting	1 hour
Self-Management: Problem solving, Social support, Environmental rearrangement, Self- monitoring, Action planning	1 hour
Operations: Office tour, Supplies (obtain laptop, office supplies, keys, office space, business cards, parking card), Building access, Job description, Job management (evaluations, monitoring, union, hours, scheduling, payroll, meetings, supervision)	3 hours
Teams and Protocols: Geographic zones/teams, Mobile van/dentistry, Phone protocols, Assessment protocols, Mental health specialists, disease specific teams (asthma, diabetes, sickle cell disease, prematurity), Hospital protocols, Tour	4 hours
Insurance: Medicaid managed care companies, Medical neighborhoods	1 hour
Community Outreach Basics of community outreach, Community-based medical neighborhood, Tour	1 hour 30 minutes
Medical Legal Issues: Medical legal team, Social Security, Education issues (504 plans and Individual Education Plans)	1 hour
Technology: Data access, use, and support; Purple binder; Compliance and HIPAA	2 hours

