CHWs will be familiarized with the study protocol, clinic and WIC site policies, home visitation strategies, and documentation. CHWs will complete the 12-hour Mental Health First Aid course (*www.mentalhealthfirstaid.org*). [name] will then teach and practice basic motivational interviewing (4 hours). CHWs will shadow experienced CHWs on other projects at UIC for a minimum of three visits and they will shadow UIC dental clinicians for a minimum of 20 hours before being ready for field work. The first three CHW home visits will be conducted with the CHW supervisor. The CHW supervisor will score each visit using the CHW Fidelity Assessment Form (Appendix I). When the CHW scores at least 4 in each category on three visits, the CHW is ready to visit participants alone.

Phase 3: Ongoing Training

CHWs will receive continual education that includes monthly reviews of topics of interest to the CHWs, as well as participation in general CHW events conducted by the Chicago CHW Local Network (*http://chwnetwork.wordpress.com/*) and the CHECK Care Coordination team. Continual education includes oral health topics as needed (see Section 6.3.3.)

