6.3.2. CHW Supervision

CHWs are not clinicians and they often struggle with many of the same issues as their clients in terms of health problems, children, housing, and poverty. This allows them to intimately understand the challenges their clients face and usually translates into strong bonds between CHWs and clients, but it sometimes transforms into a significant burden when clients struggle with serious issues. The CHWs also must deal with the stresses of home visitation (safety, cleanliness, hectic households, and poverty) and the pressures of executing a new non-clinical role in clinical and WIC settings. In order for CHWs to successfully perform their job, they require adequate supervision and support. Supervision is best conducted using a team approach with a group of CHWs to facilitate

self-discovery and group learning. In CO-OP Chicago, CHWs will report directly to the CHW supervisor (the CO-OP Chicago project manager) for day-to-day supervision and support. [name] and the project manager will ensure the CHW roles are properly explained to clinical staff and faculty in the participating clinics. [name] will provide a similar role within the WIC sites. CHWs will meet with the CHW supervisor weekly. Every two weeks, CHWs will also meet with the CHW supervisor, [name], [name], and [name]/[name] (rotating) for discussion of clinical issues, self-management skills support, and for continuing education. [name] will meet with CHWs on an as-needed basis to discuss mental health issues related to participants or the CHW job and to generate strategies for resolution.

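### The program cost used in the ICER leaves out CHW training, supervision, continuing education and documentation time without declaring it, so cost is understated and, if the intervention works, the ICER looks too favourable

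*Combined protocol and SAP*

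**What the plan says.** Section 3.2.2 (Secondary, system-level costs) is the only place that lists the cost items. For labour it says "CHW time for visit set-up, travel, and delivery will be determined". Visit duration comes from case report forms, scheduling time from weekly estimates and transport time from mileage logs. Then "This will be multiplied by CHW salary/benefits". It adds mileage and one further line: "CHW supplies and equipment (educational materials, phones, computers, and any other items) will be obtained through expense reports". The same section states that usual care carries no additional cost.

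Appendix B gives the sources for delivery cost as mileage logs, phone logs and expense reports. Section 12.3 sums the items as program costs, separately for clinic and WIC sites, and defines the ICER as (C1 − C0)/(E1t − E0t) at 6 and 12 months. It permits one-way and multi-way sensitivity analyses but names no parameters.

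On what the program uses, section 6.3.1 says "Three to four CHWs (3.0 FTE) will be hired" and sets out post-hire training, including "CHWs will complete the 12-hour Mental Health First Aid course". Section 6.3.2 says "In order for CHWs to successfully perform their job, they require adequate supervision and support" and schedules weekly meetings with the supervisor and further meetings every two weeks with investigators. Section 6.3.3 adds supervisor-accompanied visits. Sections 6.2 and 6.3.3 require a form after each encounter.

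**The concern.** The second exploratory aim (section 3.1) is cost-effectiveness at system level. By the protocol's own account, the program cannot run on visit hours alone: CHWs must be trained before they enter the field and supervised while they work. The costing rule prices the visit and its logistics and stops there. No section says that the rest is left out on purpose, for example as start-up or research cost.

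Because C0 is zero, every hour omitted from C1 comes straight off the numerator of the ICER. The planned 95% confidence intervals do not protect against this: an item missing from the cost definition is missing from every resample. Someone using the result to plan a similar program would take the figure as the cost of running it and would budget too little.

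**Working it through.** The documents state no wage, cost total or ICER, so there is no figure to reproduce. The check has four steps.

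**1. Items side by side**

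| Resource described in sections 6.2–6.3 | Costed in 3.2.2 or Appendix B? |
|---|---|
| Visit delivery, scheduling, travel time | Yes |
| Mileage, supplies, equipment | Yes |
| Follow-up calls | Not named in 3.2.2; phone logs listed in Appendix B |
| Post-hire training and shadowing | No |
| Weekly and two-weekly meetings | No |
| Supervisor and trainer time, accompanied visits | No |
| Continuing education | No |
| Documentation after encounters | No |

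**2. Direction.** With C0 = 0 and E1 > E0 (scored so that higher is better):

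planned ICER / fuller ICER = C_counted / (C_counted + C_omitted), which is below 1 whenever C_omitted > 0.

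If the effect is zero or negative, cost is still understated, but the ICER cannot be read this way.

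**3. What the documents quantify**

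- Post-hire training per CHW (section 6.3.1): 12 h mental health course + 4 h motivational interviewing + at least 20 h dental shadowing = at least 36 h.
- Basic CHW course, only for those without earlier CHW work or training; table in section 6.3.1: 1.5 + 1 + 1 + 0.5 + 0.5 + 0.5 + 1 + 1 + 3 + 4 + 1 + 1.5 + 1 + 2 = 19.5 h. Total 36 + 19.5 = 55.5 h.
- For 3 to 4 CHWs: 3 × 36 = 108 h to 4 × 55.5 = 222 h.
- Visits offered: 420/2 = 210 families; 210 × 4 = 840 visits, or 840–1,680 h at 1–2 h each (section 6.2).
- Documentation: 840 visits + 840 calls = 1,680 encounters, so each minute of form-filling per encounter is 1,680/60 = 28 h. The time per form is not given.
- Accompanied visits: section 6.3.3 gives one in 30 and also 8%. These disagree: 840/30 = 28 visits, and 0.08 × 840 = 67. They must be reconciled before supervisor time is costed.

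**4. Illustration under assumptions that are not in the documents.** Assume 0.5–2 h set-up plus travel per visit, calls costed at 0–31 minutes (the maximum that Appendix G allows), 52 weekly and 26 two-weekly meetings of 0.5–1 h, and three shadowed visits of 1–2 h. All training is charged to one year.

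- Counted CHW hours, low: 840 + 840 × 0.5 = 1,260. High: 1,680 + 840 × 2 + 840 × 31/60 = 1,680 + 1,680 + 434 = 3,794.
- Omitted training and meeting hours, low: 3 × (36 + 3 + 78 × 0.5) = 3 × 78 = 234. High: 4 × (55.5 + 6 + 78) = 4 × 139.5 = 558.
- Addition to counted CHW labour: 234/3,794 = 6% to 558/1,260 = 44%.

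Supervisor, trainer and documentation time and the monthly topic reviews would raise this. Annualising the training would lower it, and mileage and supplies, already counted, would dilute it as a share of total cost. It shows that the omission need not be trivial; it does not estimate it.

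**The case against.** The strongest reply is that separating delivery cost from trial cost is a legitimate choice, and much of the omitted work serves the trial. CHWs are taught the study protocol, accompanied visits include fidelity scoring, and the CHW supervisor is also the project manager with trial duties. The aim is exploratory, and section 12.3 already allows sensitivity analyses. This stands in part: a declared, reasoned exclusion would be acceptable. But the plan declares none, calls the result program cost, and leaves the sensitivity analyses optional and unspecified.

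Several stronger readings are tempting but are not supported.

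- A reader might infer that follow-up calls go uncosted, since section 3.2.2 does not name them. Appendix B lists phone logs as a cost source, and the Appendix H form records start and end times and has entries for four calls. Calls are probably captured.
- A reader might compare contact hours (840 to 1,680 + 434 = 2,114) with a year of paid time for 3.0 FTE (6,240 h if one assumes 2,080 h each) and conclude that only 13–34% of paid time is costed. That ratio leaves out set-up and travel, which the plan does cost. The 2,080 h is not in the documents, and delivery runs over more than one year because sites are randomized as they fill.
- A reader might add the 4.5 h pre-hire course. It is given to candidates before posts are advertised, and nothing says it is paid time.
- A reader might suppose that payroll and supervision records already exist to correct the cost. No section describes them.

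**Conclusion.** The point holds. Followed as written, the plan omits from program cost the training, recurring supervision, continuing education and documentation that it describes elsewhere as part of the program, and nothing on the comparator side offsets this. The understatement of cost runs in one direction. That the ICER is too favourable depends on a positive effect. The size cannot be derived: the firm figures are at least 36 h of post-hire training per CHW, and 55.5 h for those new to the role. The 6–44% addition to CHW labour rests wholly on the assumptions listed with it. The primary analysis and the clinic-versus-WIC aim are untouched, so this is a worthwhile improvement to an exploratory analysis, not a threat to the trial's main conclusion.

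**What to change.** In sections 3.2.2 and 12.3, define C1 to include CHW, supervisor and trainer time for intervention-related training (annualised), supervision, continuing education and documentation, alongside the items now listed. Name follow-up call time explicitly. Add a source for these hours to Appendix B.

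State what is excluded as research-only: study-protocol familiarization, trial fidelity scoring, the project manager's trial duties, and the courtesy visits offered to usual-care families after final data collection (section 7.8). For this reason, raw payroll for 3.0 FTE should not simply replace the current sum.

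Report the ICER with this cost, and with the currently listed cost as a pre-specified sensitivity analysis.

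The price is modest but real. Meeting and training time must be logged as it happens, because it would be hard to reconstruct later. Supervisor time must be apportioned between delivery and research by a stated rule. With a positive effect, the headline ICER will be less favourable. Participants and the primary analysis are not affected.
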